4.1 Hypothesis

In subjects with adult ADHD after Mydayis treatment (from end of single-blind placebo lead-in) there will be significant improvement in:

1) Overall symptoms of adult ADHD as measured by the total score on the Adult ADHD Investigator Symptom Rating Scale (AISRS) (primary effect).

2) Overall inattentive (IA) and hyperactive-impulsive (HI) ADHD symptom subsets on the AISRS and overall impairment via the Clinical Global Impression-Severity (CGI-S) scale.

3) Total ADHD symptoms fourteen hours after AM dosing as measured via total scores on the Time Sensitive Adult ADHD Symptom Scale (TASS); Inattentive (IA) and hyperactive-impulsive (HI) ADHD symptom subsets (TASS) subsets.

4) In neuropsychological measurement of Executive Function in the early evening (fourteen to fifteen hours after morning dosing) as measured by (WebNeuro: Verbal Interference/Stroop, Go/No-Go, CPT/TOVA)

5) In clinical symptoms of Executive Function in the early evening, as measured by the BRIEF-A.

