Eligible participants will return to the study site for the placebo-baseline visit within 21 days of Visit1. In some cases subjects can be on hold for 90 days with bimonthly check ins. Study staff will review inclusion and exclusion criteria and the results from the ECG, laboratory testing, and urinalysis. The following procedures and assessments will be performed during Visit 1: vital signs, AISRS, Expanded ASRS, CGI-S, and TASS. Concomitant medications and adverse events (AE), if any, will be noted.

Eligible participants will begin the second week of the single-blind placebo lead-in. Participants will be instructed to take the single-blind placebo the next morning and continue to take IP once daily in the morning and to return all unused caps capsules at the next study visit. The TASS will be done three times on days of administration. The recommended dosing is at 5 am +/- 1 hour. The first TASS is done at half hour to one hour post dose (5:30 to 6 am +/- 1 hour), the second TASS is done 4 hours post dose (9am +/- 1 hour) and the third TASS is done 14-15 hours post dose (7pm+/- 1 hour). All TASS administrations will be via telephone.

Single-Blind Placebo Baseline Lead-in (Week 2, Visit 3): takes approximately two and a half hours.

Participants will return to the study site to finish the second week of placebo lead-in within 7 days of Visit 2. The following procedures and assessments will be performed at

Visit 2: vital signs, AISRS, CGI-S, WebNeuro battery assessments (Verbal Interference/Stroop, Go/No-Go, CPT/TOVA), TASS, Expanded ASRS, C-SSRS and BRIEF-A. Concomitant medications and AEs, if any, will be noted. Drug accountability and compliance will be performed.

Participants with \geq 30% decrease in total AISRS scores during the placebo lead-in will be considered placebo responders and discontinued from the study.

All other participants will be prescribed 12.5mg of Mydayis. They are instructed to take the study medication once daily at 5 am in the morning and to return all unused medication at the next study visit.

The TASS will be done three times on days of administration. The recommended dosing is at 5 am +/- 1 hour. The first TASS is done at half hour to one hour post dose (5:30 to 6 am +/- 1 hour), the second TASS is done 4 hours post dose (9am +/- 1 hour) and the third TASS is done 14-15 hours post dose (7pm+/- 1 hour). All TASS administrations will be via telephone.

Treatment Phase- Hybrid Visits

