6.4.2 Sample Size Considerations

Justification for sample size: Up to 50 patients will be enrolled to be sure that 32-30 evaluable patients reach the end of treatment at week six. The graph shows power at different values of the Cohen's d effect size for estimating the difference between baseline and endpoint values. Our primary analysis, which uses a two-sided test with a type I error of 0.05, shows that 32 evaluable patients will give power of 90% or more for effect sizes of 0.6 or greater. 0.6 is a reasonable expectation for an effect size; it is half of the 1.2 effect size reported by *Spencer et al.* (2008) and thus is at the lower end of what we should expect to see in this study.

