6.4.3 Planned Analyses

6.4.3.1 Primary Analyses

Our statistical analysis framework will be the general linear regression model. We will choose the distributional family and link function based on the distribution of the outcome variables. Each regression model will predict the outcome as the dependent variable with weeks in trial after the end of the single-blind placebo lead-in as the independent variable. All analyses will use the ITT sample. For our design, a significant effect of week assesses the significance of the drug effect. We have chosen an IIT analyses as we can include all patients except for placebo responders in the analyses. We have chosen a single-blind placebo lead-in to define placebo responders, which are defined as patients who experience \geq 30% decrease in their total AISRS scores during placebo lead-in treatment and will be discontinued from the protocol. We anticipate that, based on the literature, 10% or fewer of patients will be placebo responders and that the overall discontinuation rate in the trial will be 20% (*Manor et al. 2012*). The changes within the day in TASS ratings, 1-hour post dose vs. 4 hours post dose vs. 14-15 hours post dose will also be analyzed via the general linear regression model. Correlations between ADHD and executive function ratings will be examined via Spearman's correlation coefficients.

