6.4.3.4 Analysis of Subject Characteristics

All subjects will be entered into the analysis including:

All-randomized population: Any subject randomized into the study, regardless of whether they received study drug

All-treated population: Any subject randomized into the study that received at least one dose of study drug

Protocol-compliant population: Any subject who was randomized and received the protocol required study drug exposure and required protocol processing

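### The set called ITT drops placebo responders on what appears to be the same AISRS score that serves as baseline, which modestly inflates the week effect and the type I error

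*Combined protocol and SAP*

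**What the plan says.** The AISRS total is the primary outcome in 4.1, 5.1 and 6.4.4, and I take it as such here, although 6.4.1 names correlations instead.

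- **Baseline.** Section 4.1 expects that "after Mydayis treatment (from end of single-blind placebo lead-in) there will be significant improvement in" the AISRS total. The regression in 6.4.3.1 uses "weeks in trial after the end of the single-blind placebo lead-in as the independent variable", and a significant week effect is read as the drug effect. Section 6.1.3 says there is no randomization, so there is no concurrent control.
- **Analysis set.** All analyses are to use the ITT sample, described as "We have chosen an IIT analyses as we can include all patients except for placebo responders in the analyses". The same description is in 5.1, 6.4.1 and 6.4.4.
- **Removal rule.** In 6.3.5, patients with a fall of 30% or more are removed: "decrease in total AISRS scores during the placebo lead-in will be considered placebo responders and discontinued from the study". The matching sentence in 6.3 measures the fall from Visit 1 to Visit 2.
- **Expected numbers.** Section 6.4.3.1 anticipates that 10% or fewer will be placebo responders. Section 5.3 plans for 34 to enter the lead-in and 32 to enter treatment.
- **Missing data.** Section 6.4.5 carries the last observation forward.

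No section provides a second baseline AISRS, an average over the lead-in, or a correction for regression to the mean.

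**The concern.** A patient whose end-of-lead-in AISRS happens to be low is more likely to meet the 30% rule and be removed. Those who stay have end-of-lead-in scores that are, on average, too high by measurement error. Their next scores drift back down with no drug effect. With a control arm this would cancel between arms. Here all of it goes into the week effect, always in favour of Mydayis.

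The label is a separate matter. A set that excludes people on an outcome measured after they took study product is not ITT in the usual sense, and a reader of the results would be misled.

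**Working it through.** **1. The plan's own figure.** Section 6.4.2 uses a "two-sided test with a type I error of 0.05" and states that "32 evaluable patients will give power of 90% or more for effect sizes of 0.6 or greater", for "estimating the difference between baseline and endpoint values". A paired t-test with n = 32 and d = 0.6 has noncentrality 0.6 × √32 = 3.394 on 31 df, which gives power of 90.8%. The figure reproduces, and it confirms that the powered contrast is within-patient, baseline to endpoint.

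**2. Which score selects.** The sentence in 6.3 giving Visit 1 to Visit 2 stands under the heading for lead-in week 2, Visit 3. The procedures that text lists for Visit 2 include WebNeuro and BRIEF-A. The visit schedule places those at Visit 3 and not at Visit 2. Section 6.3.5 has the same mismatch and applies the rule to the lead-in as a whole. The second score is therefore most consistently the end-of-lead-in AISRS, which is also week 0.

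**3. Approximate size.** Let each score be a stable true value plus independent visit error with SD s, and treat the rule as a cut on the fall D from start to end of lead-in. Then SD(D), given the true value, is √2·s, and the covariance of the end-of-lead-in error with D is −s². If a fraction r is removed:

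- mean error left in the retained baseline = (s/√2) × φ(z_r)/(1−r)
- SD of the later change ≈ √2·s
- spurious d = 0.5 × φ(z_r)/(1−r)

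At r = 10%, d = 0.5 × 0.1755/0.9 = 0.097, and a two-sided paired test at n = 32 rejects 8.3% of the time. At the planned flow, r = 2/34 = 5.9%, d = 0.5 × 0.1173/0.941 = 0.062 and rejection is 6.3%.

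**4. Simulation with the actual percentage rule.** No drug effect, 400,000 patients per scenario. The AISRS total runs 0-54 (18 items scored 0-3, section 6.2). Mean 38, SD 8 and visit correlation 0.4-0.8 are assumptions.

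| Removed | Spurious fall (points) | d, paired | Rejection, paired | Rejection, week 0-4 slope |
|---|---|---|---|---|
| 5% | 0.28-0.55 | 0.06-0.07 | 5.9-6.5% | 5.6-6.1% |
| 10% | 0.51-1.00 | 0.105-0.12 | 8.9-10.2% | 7.6-8.7% |
| 20% | 0.92-1.73 | 0.19-0.21 | 18.5-21.5% | 15.6-17.5% |

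With SD 7-9, correlation 0.5-0.8 and a mean lead-in drop of 0-4 points, the combinations that remove about 7-12% give roughly 0.4-1.1 points and d 0.07-0.14. Rejection is about 7-11% (paired) or 7-10% (slope). If patients also differ lastingly in placebo response (SD 3-5 points), 10% removed gives d 0.08-0.11 and paired rejection of 7.5-8.9%.

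**5. If the week-1 score selects instead.** With independent visit errors, d is 0.00 and rejection is 5%. With error autocorrelation 0.5, d is about 0.05 and rejection about 6%.

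**6. Does the remedy work?** Example: SD 8, correlation 0.6, lead-in drop 3. About 9.6% are removed and the spurious change is −0.75 points.

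- Adding responders back under LOCF gives each a change of zero, so the bias is only −0.75 × (1 − 0.096) = −0.68.
- A likelihood analysis using the lead-in scores of all entrants, with responders' later values missing, brought the bias to within 0.04 points.

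**The case against.** **The selecting score may not be the baseline.** By the current schedule, Visit 2 is lead-in week 1, and a literal reading of 6.3 removes most or all of the bias. Nor does 6.4.3.1 say outright that the end-of-lead-in score enters the regression; with weeks 1-4 only there would be no artefact. This stands as a condition on the finding. Section 4.1 and the powered contrast in 6.4.2 still point to an end-of-lead-in baseline.

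**The effect is small.** At 10% removed it is 0.10/0.6, about one sixth of the design effect. That is correct. A reader might infer that a positive result could be produced by selection alone, but at the plan's own responder rate the figures do not support that. A reader might also set favourable rejections against 2.5% and report a several-fold inflation. The planned test is two-sided at 5%, so that is the level to compare with.

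**Excluding responders defines the target population.** They are discontinued before any Mydayis, and the plan states the exclusion openly. Enrichment of this kind is legitimate. The fault lies in using one score for two purposes and in the name ITT.

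**Section 6.4.3.4 might be read as contradicting the exclusion**, since it says "All subjects will be entered into the analysis including" several populations. It concerns subject characteristics, so it is weak evidence about the primary set.

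**Conclusion.** The concern holds in a conditional and moderate form. If the end-of-lead-in AISRS both selects and serves as baseline, which is the most consistent reading, the primary estimate is biased toward the drug by about 0.4-1.1 points when 7-12% are removed. The two-sided type I error is then about 7-11% (paired) or 7-10% (slope), and about 6-6.5% when 5-6% are removed. It grows quickly if more patients respond to placebo. These figures rest on assumed AISRS mean, SD and correlation; d and the rejection rates change little with the correlation. The ITT label is wrong whatever the size of the bias. This should be corrected, but it does not invalidate the trial.

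A reader might also infer that the correction restores a true 5% test of drug effect. It does not: drift over time and ratings by staff who know the treatment (6.1.4) still load on the week effect.

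**What to change.** 1. Reconcile the visit labels in 6.3 and 6.3.5 so that the two AISRS scores used by the responder rule are unambiguous, and name the visit that supplies the baseline AISRS.
2. Specify a likelihood-based repeated-measures model of AISRS that includes the lead-in visits (1-3) of everyone who enters the lead-in. Leave responders' treatment-phase values missing, and do not apply the LOCF rule of 6.4.5 in this analysis.
3. Keep the set without responders as a supplementary analysis under a name other than ITT.
4. Report the number of responders removed and their lead-in change.

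**Cost.** No new data are needed, because AISRS is already scheduled at Visits 1, 2 and 3. It is more than a change of label: the plan now contains neither this model nor an exception to LOCF. The estimate would refer to all lead-in entrants, including responders never given Mydayis, and would rely on missing-at-random given the lead-in scores. For responders that assumption is well supported, because removal follows recorded AISRS values.

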5.1 General Design Description

Description of Study type

This will be a phase three, single-blind study, with a two-week, placebo lead-in and then a four-week forced titration treatment with Mydayis with starting dose of 12.5 mg/day with titration based on clinical response and potential adverse events.

Number and Description of Each Treatment Arm/Group

This will be a six-week trial after the screening period. After a two-week, subject singleblind, placebo lead-in, all patients will receive four weeks of Mydayis (12.5mg-37.5mg/day), with treatment order fixed. Study visits are hybrid; conducted remotely and in clinic.

Doses per Subject per Treatment

During the two-week, placebo lead-in, all subjects will receive 12.5mg Placebo at Visit 1 and Visit 2. During Visit 3, Mydayis treatment will be initiated at a dose of 12.5mg/day and will increase in increments of 12.5mg, based upon clinical response and tolerability, up to 25mg at Visit 4, up 37.5mg at Visit 5 and holding at the dose from visit 5 of up to 37.5mg at Visit 6. There will be no dispensation at Visit 7, which is the last in clinic/remote visit for this study. Patients will be seen weekly throughout the trial both in clinic and remote.

Our primary outcome is effects of Mydayis on overall adult ADHD symptoms via total AISRS Score. In secondary analyses, we will also analyze the following variables: Evaluation of ADHD subset IA and HI symptoms on the AISRS; TASS scores 1 hour, 4 hours and 14-15 hours post dose (total, inattentive and hyperactive-impulsive subsets) (for effects of Mydayis over time at different points of the day and within the day); expanded Adult ADHD Self Report Symptom Rating Scale (expanded-ASRS) Symptom Checklist (total, inattentive and hyperactive-impulsive, executive function and emotional control subsets); symptoms of executive function (BRIEF-A: GEC, metacognition, behavioral regulation scales and subscales: Inhibit, Shift, Emotional Control, Initiate, Working Memory, Plan/Organize, Organization of Materials, Monitor); and neuropsychological tests (WebNeuro: Verbal Interference/Stroop, Go/No-Go, CPT/TOVA): Response Time Variability [RVP], Response Time, d', Errors of Omission, Errors of Commission, Post-Commission Response Times, Multiple Responses, Anticipatory Responses).

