1st Dosing information; At the end of Visit -1, eligible participants will begin the singleblind placebo lead-in. Participants will be instructed to take the single-blind placebo the next morning and continue to take IP once daily in the morning and to return all unused capsules at the next study visit. The TASS will be done three times on days of administration. The recommended dosing is at 5 am +/- 1 hour. The first TASS is done at half hour to one-hour post dose (5:30 to 6 am +/- 1 hour), the second TASS is done 4 hours post dose (9am +/- 1 hour) and the third TASS is done 14-15 hours post dose (7pm+/- 1 hour). All TASS administrations will be via telephone.

Placebo Lead-in Phase

Single-Blind Placebo Baseline Lead-in (Week 1, Visit 2)

Eligible participants will return to the study site for the placebo baseline visit within 21-90 days of Visit -1. If unable to come in within the 21 day range, subject will reconsent monthly and have some screening measures redone as per principal investigator discretion. Study staff will review inclusion and exclusion criteria and the results from the ECG, laboratory testing, and urinalysis. The following procedures and assessments will be performed during Visit 1: vital signs, AISRS, Expanded ASRS, CGI-S, and TASS. Concomitant medications and adverse events (AE), if any, will be noted.

At the end of Visit 1, eligible participants will begin the single-blind placebo lead-in. Subjects will be instructed to take the single-blind placebo the next morning, to continue to take IP once daily in the morning and to return all unused capsules at the next study visit. The TASS will be done three times on days of administration. The recommended dosing is at 5 am +/- 1 hour. The first TASS will be done at half hour to one-hour post dose (5:30 to 6 am +/- 1 hour), the second TASS will be done 4 hours post dose (9am +/- 1 hour) and the third TASS will be done 14-15 hours post dose (7pm+/- 1 hour). All TASS administrations will be via telephone.

Single-Blind Placebo Baseline Lead-in (Week 2, Visit 3)

Participants will return to the study site for the second week of Placebo baseline visit within 7 days of Visit 1. The following procedures and assessments will be performed at Visit 2: vital signs, AISRS, CGI-S, WebNeuro battery assessments, TASS, Expanded ASRS, C-SSRS and BRIEF-A. Concomitant medications and AEs, if any, will be noted. Drug accountability and compliance will be performed.

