6.4.3.2 Secondary Objectives Analyses

In secondary analyses, we will also analyze the following variables: Evaluation of ADHD subset IA and HI symptoms on AISRS, TASS 1 hour, 4 hours and 14-15 hours post dose: (total, inattentive and hyperactive-impulsive subsets) (for effects of Mydayis over time at different points of the day and within the day); expanded Adult ADHD Self Report Scale (ASRS) Symptom Checklist (total, inattentive and hyperactive-impulsive, executive function and emotional control subsets); symptoms of executive function (BRIEF-A: GEC, metacognition, behavioral regulation scales and subscales: Inhibit, Shift, Emotional Control, Initiate, Working Memory, Plan/Organize, Organization of Materials, Monitor); and neuropsychological tests (Stroop: Color, Word and Interference Score; and TOVA: Response Time Variability [RVP], Response Time, d', Errors of Omission, Errors of Commission, Post-Commission Response Times , Multiple Responses, Anticipatory Responses).

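### The within-day TASS comparison specifies no placebo-day reference at the same clock times, so it cannot test whether the Mydayis effect differs between hours

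*Combined protocol and SAP*

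**What the plan says.** **The analysis.** Section 6.4.3.1 states that "changes within the day in TASS ratings, 1-hour post dose vs. 4 hours post dose vs. 14-15 hours post dose will also be analyzed" by the general linear regression model. Sections 5.1, 6.4.1 and 6.4.4 carry the same sentence with trivial differences. None of the four says which visits enter the comparison or names a term for placebo versus Mydayis. The only independent variable named is time, "with weeks in trial after the end of the single-blind placebo lead-in as the independent variable", and the drug effect is inferred from it: "a significant effect of week assesses the significance of the drug effect".

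**The interpretation.** Section 6.4.3.2 lists the TASS at the three times after dose "for effects of Mydayis over time at different points of the day and within the day". Sections 5.1 and 6.4.4 attach the same purpose to it.

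**The data.** Sections 6.3 and 6.3.5 set dosing at 5 am +/- 1 hour, and 6.1.8 says that the assessments depend on it. "The TASS will be done three times on days of administration", at about 5:30-6 am, 9 am and 7 pm. The evening rating is described in the same words in the placebo lead-in and in the treatment phase: "the third TASS is done 14-15 hours post dose (7pm+/- 1 hour". The schedule table marks TASS at both lead-in visits and at Visits 4 to 7.

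**The reference point.** The hypotheses in 4.1 measure improvement from the end of the placebo lead-in.

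**The concern.** Duration is in the trial's title, and re-examining late-day efficacy by TASS is a declared purpose (1.1, 3.2). Three ratings in a day cannot show by themselves how a drug effect rises or falls. Because everyone takes the capsule at about 5 am, 1 h, 4 h and 14-15 h after dose are also just awake, mid-morning and early evening. Symptoms may differ between those times with no drug at all.

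If symptoms naturally worsen by evening, a constant effect will look as if it wanes. If they naturally ease, an effect that has worn off may look as if it lasts. The design schedules the control that would separate the two, namely the same patients' placebo-day ratings at the same clock times. The plan does not say that the within-day comparison uses them.

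**Working it through.** **1. The plan's own figure.** The only power statement (6.4.1, 6.4.2) is for the primary baseline-to-endpoint comparison: 90% or more with n = 32, d = 0.6 and two-sided alpha 0.05. For a paired t test, df = 31, the critical value is 2.040 and the noncentrality is d × √n = 0.6 × √32 = 3.394. Power is 90.8%, so the figure reproduces. No power is stated for the within-day TASS comparison.

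**2. What each contrast estimates.** Write c(h) for the no-drug symptom level at clock time h and e(h) for the drug effect at that time. Assume c(h) is the same in both phases. A placebo-day rating then has mean c(h), and a drug-day rating has mean c(h) + e(h).

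- Within-day on drug days: [c(14) − c(4)] + [e(14) − e(4)]. The first bracket is drift, and it enters point for point.
- Same hour, drug minus placebo: e(14). This shows whether an effect is present in the evening, not whether it differs from the effect at 4 h.
- Difference of the two within-day changes: e(14) − e(4). Drift cancels.

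Adding hour to a model with week, without an interaction, does not help. Take Visits 3 to 7 as one placebo visit and four drug visits with equal weight, and a within-day change in effect that is equal at all four. The hour term then estimates drift + (4/5) × [e(14) − e(4)], so drift still enters in full.

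**3. Illustration of size.** The documents give no TASS drift and no SD of the within-patient 4 h to 14-15 h difference, so both are assumed. With n = 32, drug-day data only and e(14) = e(4), the noncentrality is (drift/SD) × √32. For drift 3 and SD 8 it is 0.375 × 5.657 = 2.121, which gives 54%. Probability of a two-sided significant result at 5%:

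| Assumed SD | Drift 2 | Drift 3 | Drift 4 |
|---|---|---|---|
| 6 | 45% | 78% | 95% |
| 8 | 28% | 54% | 78% |
| 10 | 20% | 38% | 59% |

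The error also runs the other way. A true loss of effect of 0.6 SD would be detected 90.8% of the time without drift. Offset by a natural evening easing of 0.3 SD, it leaves a net 0.3 SD and is detected 37.6% of the time. Offset by 0.6 SD, it is detected 5% of the time.

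**4. Price of the placebo-referenced contrast.** Assume equal SDs on placebo and drug days and correlation ρ between a patient's two within-day changes. The SD is then multiplied by √(2(1 − ρ)). For a true change in effect of 0.6 SD:

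| ρ | SD multiplier | Power at n = 32 | n for 90% |
|---|---|---|---|
| 0 | 1.414 | 64% | 61 |
| 0.3 | 1.183 | 79% | 43 |
| 0.5 | 1.000 | 91% | 32 |
| 0.7 | 0.775 | 99% | 20 |

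The documents do not give ρ.

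**5. Are the reference ratings clearly placebo-day ratings?** The schedule table puts lead-in weeks 1 and 2 at Visits 2 and 3 and marks TASS at both. In 6.3 and 6.3.5, the text under the week 2, Visit 3 heading lists its procedures as being done at Visit 2. The TASS visit list in 6.3 has V1 and V3 to V7 but no V2, and it comes directly after Mydayis is prescribed. Which capsule precedes the V3 ratings therefore has to be settled.

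**The case against.** The strongest reply is that the duration question already has a same-clock-time placebo reference. Section 4.1 measures TASS improvement at fourteen hours from the end of the lead-in, and the regressions run on weeks since that point. If that visit is week 0, 7 pm on Mydayis is compared with 7 pm on placebo and common drift cancels. This stands. A reader might infer that the trial must get its evening result wrong, but the documents do not support that. The reply does not reach the question of whether the effect differs between hours: a significant result at 4 h beside a non-significant one at 14-15 h is not a test of waning.

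Second, a reader might infer that the plan excludes the placebo ratings, or commits itself to reading a raw within-day difference as waning. It does neither. It is silent on which days enter and on how the result will be read, beyond attributing it to Mydayis. A model with both week and hour is a possible reading, but without an interaction it leaves the problem in place (step 2). The appendix list also names a Statistical Analysis Plan for 6.4.1 whose text is not in the combined document, so the point covers only what the protocol's own sections specify.

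Third, drift and SD are assumptions, neither the existence nor the direction of drift is shown, and TASS is secondary. All true. The rejection rates are illustrations, and counting them as false positives presumes that the contrast is read as a drug effect. The identity that bias equals drift does not depend on the assumed values.

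**Conclusion.** The point holds in a limited form. As written in 5.1, 6.4.1, 6.4.3.1 and 6.4.4, the within-day TASS comparison specifies no use of the lead-in profile, so it cannot separate the drug's time course from ordinary change between early morning and evening. Its bias equals that change, of unknown size and sign. Over assumed drifts of 2 to 4 points and SDs of 6 to 10, a constant drug effect would give a significant within-day difference in 20% to 95% of trials of 32 patients.

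Statements on onset, persistence or waning would rest on an invalid contrast. Presence of an effect at 14-15 h can still be addressed hour by hour, provided the end of the lead-in is week 0, which the plan should state. No stated figure is wrong and the primary comparison is unaffected. The change should be made because it is cheap and duration is a stated aim.

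**What to change.** 1. Reconcile the visit labels and the TASS visit list across the schedule table, 6.3 and 6.3.5, so that the reference ratings are clearly those taken on placebo at the end of the lead-in.
2. In 5.1, 6.4.1, 6.4.3.1 and 6.4.4, replace the within-day sentence with one repeated-measures model for TASS at the three hours, with phase (end of placebo lead-in versus Mydayis), time of day and their interaction. Make Visit 7 versus the end-of-lead-in visit the key contrast; the other treatment visits may stay in the model.
3. Base any statement on onset, persistence or waning on the interaction, and show the placebo-day and drug-day profiles side by side.
4. State that the end of the lead-in is week 0 in the per-hour regressions.

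The cost is wording; no new visit or rating is needed if step 1 confirms that the end-of-lead-in ratings are placebo-day ratings. With equal SDs, the standard error is larger than that of the raw contrast unless the placebo-day and drug-day changes correlate at about 0.5 or more; power for a 0.6 SD change could be as low as 64% at a correlation of 0. The contrast does not remove calendar-time or expectancy effects of the fixed-order, single-blind design: any part that differs between hours stays in the interaction, and the phase difference at a single hour carries them in full.
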